4.3.2 Secondary Efficacy Endpoint

For the secondary efficacy objective (durability of efficacy at 36 months and at 48 months), the endpoints are defined as for the primary efficacy endpoint (i.e., sustained QFT conversion [Section 4.3.1]).

Two mITT durability analyses will be performed: the first one after all participants have at least 36 months of follow-up (or have discontinued the study early) and the second one at study completion when all participants have 48 months of follow-up (or have discontinued the study early) (Section 9.3). For the secondary analysis after 36 months of follow-up, all participants will have a data cutoff date corresponding to their Month 36 visit date or their early discontinuation date if it occurred prior to Month 36 visit.

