7 OVERALL STATISTICAL CONSIDERATIONS

7.1 Research Hypotheses

Primary: Revaccination with BCG reduces the risk of sustained *Mtb* infection (defined for this protocol as sustained QFT conversion) versus placebo in previously BCG vaccinated, QFT negative healthy adolescents.

Secondary (hierarchical):

- Revaccination with BCG reduces the risk of sustained *Mtb* infection versus placebo in previously BCG vaccinated, QFT negative healthy adolescents, with vaccine efficacy (VE) durability that lasts at least 36 months.
- Revaccination with BCG reduces the risk of sustained *Mtb* infection versus placebo in previously BCG vaccinated, QFT negative healthy adolescents, with VE durability that lasts at least 48 months.

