7.8 Multiplicity

The primary analysis will be triggered when at least N=118 sustained *Mtb* infection events (defined as QFT conversion from a negative to positive test result, as per QuantiFERON-TB Gold Plus Package Insert) in the mITT efficacy population have accrued.

The primary efficacy endpoint (Section 4.3.1) will be analyzed using a log-rank test, stratified by sex and age group (10-11 years old, 12-14 years old, and >14 years old) to evaluate differences in the distributions of event times between the BCG vaccination and placebo groups. The two durability analyses will be performed: the first one after all participants in the mITT efficacy population have either prematurely discontinued the study or have at least 36 months of follow-up (secondary analysis; a data cutoff date will be established at the date of each participants Month 36 visit) and the second one after all participants in the mITT efficacy population have completed 48 months of follow-up at the end of study (final analysis).

Therefore, the following null hypotheses: $H_{01} \rightarrow H_{02} \rightarrow H_{03}$ will be assumed:

- H_{01} corresponding to the primary analysis (at least N=118 sustained QFT conversion events in the mITT efficacy population have accrued): $S_{s,BCG}(t) = S_{s,Pbo}(t)$
- H_{02} corresponding to the secondary analysis (when all participants have prematurely discontinued the study or have at least 36 months of follow-up): $S_{s,BCG}(t) = S_{s,Pbo}(t)$
- H₀₃ corresponding to the final analysis (when all participants have prematurely discontinued the study or have completed the study with 48 months of follow-up): S_{s,BCG}(t) = S_{s,Pbo}(t)

for strata s=1, 2, ..., 6 (6 strata = sex and age group [10-11 years old, 12-14 years old, and >14 years old]), where S(t) is the survival probability (probability that a participant's time to sustained *Mtb* infection > t).

To account for multiple testing, a step-down approach will be used to preserve the overall Type I error at a one-sided 2.5%. Specifically, if the one-sided p-value associated with the primary hypothesis H_{01} of BCG vaccine efficacy relative to placebo (p_1) is less than or equal to 0.025, the durability of the vaccine efficacy after all participants have 36 months of follow-up (H_{02}) will be formally assessed. If both H_{01} and H_{02} are rejected at one-sided 2.5% then the H_{03} will be formally assessed at one-sided 2.5%.

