9 EFFICACY ANALYSES

9.1 **Primary Analysis**

The primary efficacy endpoint will be analyzed when at least N=118 sustained *Mtb* infection events (defined as QFT conversion from a negative to positive test result, as per QuantiFERON-TB Gold Plus Package Insert) in the mITT population have accrued.

The primary efficacy endpoint (sustained QFT conversion as defined in Section 4.3.1) will be analyzed using a log-rank test, stratified by sex and age group (10-11 years old, 12-14 years old, and >14 years old) to evaluate differences in the distributions of event times between the BCG vaccination and placebo groups.

Censoring and event times will be defined as follows:

- For participants with sustained QFT conversion (censor = 0), time to event will be derived in days as (date of initial conversion date of Day 71 +1) and converted to months. Note that Day 71 here refers to either Day 71 or, if missed, the first in-person visit after Day 71. Date of initial conversion = date of a positive QFT test observed after a negative result at Day 71 or after a negative test at the first in-person visit after Day 71 if the Day 71 visit was missed.
- For participants without sustained QFT conversion (censor = 1), censoring time will be derived in days as (censoring date date of Day 71 + 1) and converted to months. Again, Day 71 refers to either Day 71 or, if missed, the first in-person visit after Day 71.

The censoring date for participants without sustained QFT conversion is the last date at which a non-missing QFT result is available prior to the date of data cut-off. There are several scenarios in which participants may have an initial QFT conversion but fail to meet the requirements for sustained QFT conversion due to subsequent negative, missing, or indeterminate QFT results. Appendix 6 provides details on derivation of event and censoring times for all the expected possible scenarios.

Conventions for additional scenarios not covered in Appendix 6, but based on actual data may need to be considered and detailed in the ADaM specifications prior to all planned analyses. An indeterminate test result will be interpreted as negative for the derivation of a participant's time to event.

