The Cox-model estimate of the log-hazard ratio and its standard error will be used to construct a modelbased estimate of the confidence limits on the HR. The confidence limits are first constructed for the log HR and then exponentiated to provide the corresponding confidence limits on the HR scale. In case of ties in reporting event times, the Efron option in the SAS procedure PHREG will be used.

The log HR estimate obtained from the Cox proportional hazard model is a consistent (asymptotically unbiased) estimate. However, the Cox-model based estimate of the standard error is biased when the proportional HR model assumption does not apply. Thus, if the test for the statistical significance of the coefficient associated with the interaction of survival time and treatment group is nominally significant at the 0.10 level, then the robust sandwich estimate (Li and Wei [1989]; Lachin [2000]) will be employed to provide a consistent estimate of the variance of the log HR estimated from the proportional HR model. The resulting robust confidence limits on the HR will then have the desired coverage probability even though the proportional HR assumption may not apply for the treatment effect.

Vaccine efficacy will be calculated as $VE = 1 - Hazard Ratio \left(\frac{BCG}{Placebo}\right)$

The 95% CI for vaccine efficacy will be derived using the HR CI as follows:

- $VE_{lower limit} = 1 Hazard ratio_{upper limit}$
- VE_{upper limit} = 1 Hazard ratio_{lower limit}

The following information will also be summarized in tables for the mITT efficacy population and repeated for the PP efficacy population:

- Initial QFT conversions by calendar month (mITT efficacy population only).
- Sustained conversion rates with 95% confidence intervals for each treatment group. 95% CIs will be constructed based on the Miettinen and Nurminen method without stratification (Miettinen O, Nurminen [1985]).
- Overall sustained conversion incidence rates along with 95% CIs will be determined based on the total event/censoring time used as denominator. The sequence of sustained conversions will be modelled to follow approximately a Poisson process with constant

intensity θ . The rate parameter θ will be estimated as $\lambda = D/T$, where $T = \sum_{j=1}^{n} t_j$ and D is

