the number of participants with a sustained conversion and time t_i (i=1,...n) is the time to sustained conversion if observed, or if not observed, the censored time. Conditional on T, an exact 100*(1- α)% confidence interval for a Poisson variable with parameter θ T and observed value D can be obtained using an exact 100*(1- α)% confidence interval for D/T will be derived as follows:

Lower confidence limit
$$L = \frac{0.5c_{\alpha/2,2D}}{T}$$
 for D>0, 0 otherwise,

Upper confidence limit
$$U = \frac{0.5c_{1-\alpha/2,2D+2}}{T}$$

where $c_{\alpha,k}$ is the α^{th} quantile of the Chi-square distribution with k degrees of freedom.

The following figures will be presented for the mITT efficacy population and repeated for the PP efficacy population:

• Kaplan-Meier plots for time to initial conversion and time to sustained conversion, with tick marks to identify censored observations by treatment group.

Sustained conversion rates and incidence rates will be repeated by site, age, sex, and method of reporting previous BCG vaccine subgroups for the mITT efficacy population only.

Additional listings will be produced, including whether the participant had the event or not (for initial conversion, early QFT reversion, sustained conversion, and end of trial conversion), date of event/censored date, the start date, and the time to event.

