9.3 Secondary Analyses

To address the secondary objectives (sustained QFT conversion based on positive QFT test results in participants with a follow-up of 36- and 48-months post vaccination), two analyses will be performed to assess the durability of efficacy against sustained *Mtb* infection post vaccination.

The first secondary analysis will be performed subsequent to or at the same time with the primary analysis after all participants have had at least 36 months of follow-up (or prematurely discontinued), and the second secondary (i.e., final) analysis will be performed subsequent to the initial and the 36-month analysis after all participants have 48 months of follow-up (or prematurely). Both analyses will be based on the mITT efficacy population.

Log-rank tests, stratified by sex and age group (10-11 years old, 12-14 years old, and > 14 years old), will be used to evaluate differences in the distributions of event times between the BCG vaccination and placebo groups. Hazard ratios and 95% confidence intervals will be estimated using stratified Cox proportional hazards regression models.

If the one-sided p-value after all participants have 36 months of follow-up is less than or equal to 0.025, durability after all participants have 48 months of follow-up will be assessed. As such, durability after all participants have reached 36- and 48-months of follow-up will only be concluded if statistically significant differences in event times between the BCG vaccination and placebo arms were met at all prior time points evaluated. Failure to meet the primary or 36- month durability hypothesis will not result in a formal early stopping of the study.

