Appendix 5 Prior and Concomitant Medications Date Imputation

Appendix 6 Time to Event Derivation Details

Initial QFT Conversion/ Month 3 post initial conversion/Month 6 post initial conversion ¹	Event/ Censored	Date of Event/Censoring
Sustained conversion prior to date of data cut-off (i.e. Positive/Positive/Positive: -/-/-//+/+/+/any/any)	Event	Date of Initial Conversion to QFT positive
No initial conversion prior to date of data cut-off (-/- /-//-/-)	Censored	Minimum (date of last non-missing QFT result, date of data cut-off)
Initial converters with a 3-month positive QFT and missing 6-month results prior to date of data cut-off (i.e. Positive/ Positive/missing: -/-/-//+/+/- /+/+/Missing)	Censored	Date of initial conversion to QFT positive
Initial converters with a 3-month negative QFT and missing 6-month result prior to date of data cut-off (i.e. Positive/ Negative/Missing: -/-/-//+/-/Missing)	Censored	Date of initial conversion to QFT positive
Initial converters with a missing 3-month and positive 6-month result prior to date of data cut-off (i.e., Positive/Missing/Positive: -/-//+/Missing/+)	Censored	Date of initial conversion to QFT positive
Initial converters with a missing 3-month and negative 6-month results prior to date of data cut-off (i.e. Positive/Missing/Negative: -/-/-//+/Missing/-)	Censored	Date of initial conversion to QFT positive
Initial converters with missing 3-month and missing 6-month results prior to date of data cut-off (i.e., Positive/Missing/Missing: -/-/- //+/Missing/Missing)	Censored	Date of initial conversion to QFT positive

¹indeterminate QFT results are counted a negative test result.

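### SAP 9.1 sustained-conversion incidence includes follow-up in which no event can be confirmed, and on scheduled visits the 36-month analysis reaches only conversions first detected through Month 30

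*SAP*

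**What the plan says.** **Event.** SAP 4.3.1 requires three consecutive positives: the first conversion, post-conversion (PC) Day 84, and the next biannual visit. SAP 9.1 dates the event at the first conversion and counts time from the Day 71 visit, or from its substitute if Day 71 was missed.

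**Cut-off for the 36-month analysis.** SAP 4.3.2: "all participants will have a data cutoff date corresponding to their Month 36 visit date or their early discontinuation date". SAP 7.8 repeats it: "a data cutoff date will be established at the date of each participants Month 36 visit".

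**Censoring.** SAP 9.1 censors participants without an event at the "last date at which a non-missing QFT result is available prior to the date of data cut-off". Appendix 6 has a row for "Initial converters with missing 3-month and missing 6-month results prior to date of data cut-off" and censors them at the first conversion.

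**Outputs.** SAP 9.1: "Overall sustained conversion incidence rates along with 95% CIs will be determined based on the total event/censoring time used as denominator". It also plans "Kaplan-Meier plots for time to initial conversion and time to sustained conversion, with tick marks to identify censored observations by treatment group".

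**Hypothesis.** SAP 7.1 words the first secondary hypothesis as vaccine efficacy "durability that lasts at least 36 months"; Protocol 9.1 is similar. SAP 4.3.1 and Protocol 4.3 say that a first conversion at Month 48 cannot count as sustained. Neither document says the same of Month 36.

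**The concern.** The numerator and denominator of the incidence rate cover different periods. An event enters only after about six further months of testing, whereas person-time runs to the last test. Each participant without an event therefore adds a final interval that cannot produce a numerator event. Per-arm rates come out too low, most of all when follow-up is short, as at the primary analysis. Protocol 2.1 says that this trial is to inform whether a prevention-of-disease trial is justified, so the absolute rates may be reused for planning.

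The same six-month delay limits the 36-month analysis. A first positive at Month 36 would be confirmed at about Month 39 and at Month 42, both after that participant's cut-off. A significant result could be reported as durability to 36 months although no conversion first detected after Month 30 was counted.

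**Working it through.** **Inputs** (Protocol 9.2, SAP 7.2): 1800 randomised 1:1; 7% excluded from mITT; 8-10% of the placebo arm converting per year; 70% of conversions sustained; 5% per year loss to follow-up; VE 45%. mITT per arm: 1800 × 0.93 / 2 = 837. Assumed here: constant hazards, visits on schedule, PC Day 84 attended whenever the next biannual visit is, and VE acting on sustained conversions.

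**1. The plan's own figure.** Schoenfeld's formula with HR 0.55, one-sided alpha 2.5% and 90% power gives 118 events, as stated.

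**2. Last countable visit at the Month 36 cut-off.**
- First positive at Month 30: confirmed at about Month 33 and at Month 36, so it is an event.
- First positive at Month 36: both later results are missing at the cut-off, so it is censored.

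Day 71 is 70 / 30.4375 = 2.3 months after Day 1. The at-risk window is 36 − 2.3 = 33.7 months, and events can arise only in the first 30 − 2.3 = 27.7. Without attrition, the idle share is 6 / 33.7 = 17.8%.

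**3. Incidence at Month 36, expected values** (events / person-months × 1200 = rate per 100 person-years):

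| Attack rate, arm | To last QFT | Ended at Month 30 |
|---|---|---|
| 8%, placebo | 93.3 / 23,662 → 4.73 | 93.3 / 20,075 → 5.58 |
| 8%, BCG | 52.8 / 24,349 → 2.60 | 52.8 / 20,538 → 3.09 |
| 10%, placebo | 115.1 / 23,110 → 5.98 | 115.1 / 19,700 → 7.01 |

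This is about 15-16% low. Ending time at Month 30 for everyone still leaves an idle final interval for those who discontinued earlier. Step 4 therefore ends it per participant.

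**4. Ending each non-event at their own last confirmable visit** (simulation; placebo rate per 100 person-years):

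| Analysis | 8%: as written, corrected | 10%: as written, corrected | Understated by |
|---|---|---|---|
| Primary (118th confirmed event) | about 4.5, 5.7 | about 5.4, 7.2 | 21%, 25% |
| Month 36 | 4.73, 5.72 | 5.96, 7.18 | 17% |
| Month 48 | 5.02, 5.74 | 6.31, 7.19 | 12-13% |

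The primary-analysis figures are the same for an assumed 12- or 24-month uniform accrual. The shortfall is larger at 10% because 118 events arrive sooner and the idle interval is then a larger share of follow-up.

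**5. Closed-form check.** With six-monthly testing, the placebo rate of detected sustained conversion is 0.7 × (1 − (1 − AR)^0.5) / 0.5.
- 8%: 0.7 × 0.0408 / 0.5 = 5.72 per 100 person-years (after unrounded calculation).
- 10%: 0.7 × 0.0513 / 0.5 = 7.18.

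These match the corrected Month 36 rates and not the rates as written.

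**6. Tests and VE.** Under the Month 36 cut-off no event falls after Month 30, so ending follow-up there leaves the risk set at every event time unchanged. Refitting the Cox model on simulated trials both ways gave the same log hazard ratio (difference below 1e-14). The BCG/placebo rate ratio moves by at most 0.004. The 36-month analysis would have about 145 events (8%) or 178 (10%), with power of about 0.95 or 0.98.

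**The case against.** **The limit follows from stated rules.** The three-positive definition, the cut-off and Appendix 6 are all written down, and together they imply Month 30. That stands as to derivability. But the plan spells out the consequence at Month 48, where no later visit exists, and not at Month 36, where the limit comes from a chosen cut-off.

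**SAP 9.3 plans no incidence table.** It lists only log-rank tests and Cox models for Months 36 and 48. That stands: the direct error is at the primary analysis. The later figures apply only if the 9.1 outputs are repeated, or if the primary and 36-month analyses are combined as SAP 4.2.2 allows.

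**A footnote would be enough.** It would disclose the problem but leave a table whose rates are known to be low by a fifth or more.

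A reader might infer more than the documents support:
- *That the 36-month test or VE is biased.* It is not (step 6).
- *That the 36-month null hypothesis is misworded.* SAP 7.8 states equality of survival curves. The durability wording belongs to the research hypothesis in 7.1.
- *That SAP 9.3 claims 36 months of protection.* It says "durability after all participants have reached 36- and 48-months of follow-up will only be concluded if statistically significant differences in event times" were met at earlier time points, so it refers to follow-up reached.
- *That no later conversion can ever count.* SAP 7.7 lets unscheduled QFT results contribute, so the limit holds for scheduled visits.
- *That counting Month 36 converters would show protection in Months 30-36.* The test would still be cumulative.

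**Conclusion.** Wrong as written, in two limited respects.

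(a) The person-time incidence in SAP 9.1 understates each arm's rate at the primary analysis by about 21-25%, and by about 17% and 12-13% if the output is also produced at Months 36 and 48.

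(b) On scheduled visits, the 36-month analysis covers sustained conversions first detected through Month 30, while SAP 7.1 and Protocol 9.1 word the hypothesis as at least 36 months. The corresponding Month 42 limit for the final analysis is implied by the stated Month 48 rule.

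The comparison between arms is not materially affected. The sizes rest on the planning assumptions and on those listed with the inputs; missed PC Day 84 tests are not modelled.

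**What to change.** 1. For the person-time incidence rates in SAP 9.1, and wherever they are repeated, end each non-event's at-risk time at the last scheduled visit at which a first conversion could still have been confirmed by the cut-off or last QFT. Leave the log-rank and Cox derivations unchanged, and footnote the different follow-up time.
2. On the sustained-conversion Kaplan-Meier plots, mark the last confirmable visit on the plot's own Day 71 axis. With Day 71 on schedule, the Month 30 visit is at about 27.7 months and the Month 42 visit at about 42 − 2.3 = 39.7 months.
3. In SAP 4.3.2 and 7.1, state that the 36- and 48-month analyses cover sustained conversions first detected through Months 30 and 42 on scheduled visits. Word the reported durability conclusion to match.
4. Editorial: in SAP 9.1 and Appendix 6, make the data cut-off inclusive (*on or before* instead of *prior to*). Read strictly, the present wording would drop the Month 36 result itself and move the limit to Month 24.

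**Cost.** SAP wording and programming only; no new data, no delay and no changed test. The incidence table will use slightly less person-time than the Cox analysis, and participants whose only QFT after Day 71 is Month 6 will contribute none. Allowing later results to confirm Month 36 converters is a separate option that could delay the 36-month analysis by up to six months. It is not needed for this fix.

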4.3 Efficacy Endpoints

4.3.1 Primary Efficacy Endpoint

Mtb infection is defined in this protocol as QFT conversion from a negative to positive test result, as per the manufacturer's QFT-GIT package insert.

QFT assays will be performed at:

- Screening (used to determine eligibility),
- Day 71 or at the first in-person visit after Day 71 if Day 71 visit was missed or if Day 71 result was not available.
- Every 6 months (counting from Day 1) through Month 48
- Participants who have QFT conversions from a negative to positive test result will have an additional QFT assay three months post initial conversion (Day 84 PC visit).

The primary efficacy outcome measure is sustained QFT conversion in the mITT efficacy population (Section 5.1), defined as primary QFT conversion from QFT-negative to QFT-positive, and sustained

positive QFT tests at both 3- and 6-months after initial (primary) conversion. The initial positive QFT test must be observed after a negative QFT result at Day 71 or at the first in-person visit after Day 71 for which a QFT result is available if the Day 71 visit was missed or if the QFT result at the Day 71 visit was not available.

Due to the required washout period (Section 4.1) and the many Day 71 visits missed due to COVID (lockdown, site closure, etc.), the requirement for a negative QFT test result at Day 71 was extended to include results from the first in-person visit post Day 71. Therefore, throughout this document, Day 71 refers to the Day 71 study visit, or if missing, the first in-person visit post-randomization. Sustained conversion refers to three consecutive positive QFT results following the Day 71 negative QFT result as detailed above. After the initial conversion, a negative or indeterminate result at Post Conversion Day 84 and/or at the biannual visit following the initial conversion would disqualify the conversion event from being a sustained conversion. "Early QFT Reversion" is defined as a reversion from a positive QFT test result to a negative QFT test result at Post Conversion Day 84 or the biannual visit following the initial conversion.

Participants who initially convert to QFT positive at Day 71 will be excluded from the mITT analysis population and the primary endpoint analysis.

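### The 36-month durability analysis sets the data cut-off on the Month 36 visit date but counts only results before the cut-off, so read literally it censors Month 30 conversions that the Month 36 QFT confirms.

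*SAP*

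**What the plan says.** **Cut-off.** For the 36-month analysis, SAP 4.3.2 states that "all participants will have a data cutoff date corresponding to their Month 36 visit date or their early discontinuation date" will be used. SAP 7.8 repeats the rule: "a data cutoff date will be established at the date of each participants Month 36 visit".

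**Which results count.** SAP 9.1 censors a participant without sustained conversion at "the last date at which a non-missing QFT result is available prior to the date of data cut-off". The event row of Appendix 6 reads "Sustained conversion prior to date of data cut-off" and dates the event at the initial conversion. Another row covers "Initial converters with a 3-month positive QFT and missing 6-month results prior to date of data cut-off"; these participants are censored at the date of initial conversion. The row for participants who never convert is worded differently: its censoring date is "Minimum (date of last non-missing QFT result, date of data cut-off").

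**Confirmation.** SAP 4.3.1 requires "positive QFT tests at both 3- and 6-months after initial (primary) conversion". QFT is scheduled every six months, with one extra test at post-conversion Day 84. For a conversion first seen at Month 30, the confirming tests are therefore the Day 84 test and Month 36. SAP 7.7 allows unscheduled QFT results to contribute.

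**The concern.** With one calendar cut-off for the whole trial, the difference between before and on the cut-off is a single day and hardly matters. Here the cut-off is individual, and for every participant who attends it falls on the day of a scheduled QFT. The boundary wording therefore decides whether the whole Month 36 round of tests is used to confirm conversions.

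If it is not used, a participant positive at Month 30, at Day 84 after conversion and at Month 36 has no 6-month result before the cut-off. That participant fits the Positive/Positive/Missing row and is censored at Month 30. The last conversion visit that can yield an event moves from Month 30 to Month 24.

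H02 is the first confirmatory secondary hypothesis, and H03 is tested only if H02 is rejected. The study team is to be unblinded after the primary analysis. If that analysis comes first, a boundary question left open would be settled with treatment assignments known.

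**Working it through.** **1. The passages applied to two participants attending Month 36.**

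- *Month 30 converter, positive at Day 84 and at Month 36.* Cut-off = Month 36 visit date. With an inclusive cut-off this is an event at Month 30. With a strict cut-off the 6-month result is missing and the participant is censored at Month 30.
- *Never-converter.* Section 9.1 read strictly gives the Month 30 QFT date. In Appendix 6 the minimum of the last QFT date and the cut-off date can be the Month 36 date. The two sections differ by six months for the same person.

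A first positive at Month 36 cannot be confirmed by this cut-off under either reading, so it plays no part in the comparison.

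**2. The plan's event figure.** With HR = 0.55 (VE 45%), one-sided alpha 2.5%, 90% power and 1:1 allocation (SAP 7.2), Schoenfeld's formula gives

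4 × (1.960 + 1.282)² / (ln 0.55)² = 117.6, rounded up to 118.

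This reproduces the plan. The documents give no event count for the 36-month analysis.

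**3. Inputs for expected H02 events.** From Protocol 9.2: 1800 randomised, 7% excluded at Day 71, 8–10% conversion per year on placebo, 70% sustained, 5% loss per year. mITT per arm = 900 × 0.93 = 837. My assumption: a constant hazard from Day 71 (2.30 months).

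- Monthly conversion hazard: λ = −ln(1 − 0.08)/12 = 0.00695 on placebo, and 0.55 × λ = 0.00382 on BCG.
- Expected sustained events first seen at visit v, per arm: 837 × [S(v − 6) − S(v)] × 0.70 × 0.95^((v + 6)/12), where S(t) = exp(−hazard × (t − 2.30)) and the first interval starts at Day 71. The last factor is the chance of still being in the study at the confirming visit.

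Check for Month 30 at 8%:
- Placebo: 837 × (0.8600 − 0.8249) × 0.70 × 0.8574 ≈ 17.6.
- BCG: 837 × (0.9204 − 0.8996) × 0.70 × 0.8574 ≈ 10.5.
- Sum: 28.1.

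Both arms together, by visit of first positive at 8%: Month 6, 21.9; Month 12, 33.7; Month 18, 31.7; Month 24, 29.9; Month 30, 28.1.

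**4. Power** = Φ(√(d/4) × ln(1/0.55) − 1.96), where d is the number of events.

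| Scenario | Events, inclusive | Events, strict | Lost | Power, inclusive | Power, strict |
|---|---|---|---|---|---|
| 837 per arm, 8% | 145.4 | 117.3 | 28.1 (19.3%) | 95.0% | 89.9% |
| 837 per arm, 10% | 180.1 | 145.8 | 34.2 (19.0%) | 98.0% | 95.1% |
| 1000 per arm (2150 randomised), 8% | 173.7 | 140.1 | 33.6 (19.3%) | 97.6% | 94.3% |
| 837 per arm, 8%, no loss | 161.4 | 128.6 | 32.8 (20.3%) | 96.7% | 92.4% |

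**The case against.** The strongest reply is that nobody intends to discard the Month 36 QFT, and the documents support that. Protocol 9.4.1.1 places a combined primary and 36-month analysis after all participants have completed the Month 36 visit. SAP 4.3.1 rules out only first positives at Month 48, because that is the last visit. This suggests that a final-visit QFT is meant to confirm the conversion before it. The never-converter row of Appendix 6 allows the cut-off date itself as a censoring date, and its second term would be redundant under a strict rule. Because an event is dated at initial conversion, a Month 30 event can also be called earlier than the cut-off.

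All of this stands as evidence of intent. It does not settle the text. The never-converter row does not apply to initial converters. The Positive/Positive/Missing row turns on whether the 6-month result precedes the cut-off, not on the date given to the event. Section 9.1 leaves scenarios outside Appendix 6 to the ADaM specifications, but this scenario is covered by Appendix 6.

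A reader might infer more than the documents support:

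- *That every Month 30 conversion is lost.* An unscheduled QFT may confirm one (SAP 7.7).
- *That all never-converters are censored at Month 30.* Only Section 9.1 gives that; Appendix 6 allows Month 36.
- *That H02 falls well below 90% power.* Using the 750-per-arm row of the sample-size table would suggest so, but 1800 randomised less 7% is 837 per arm. At that size the literal reading still gives about 90% at the lowest planned conversion rate.

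A missed Month 36 visit is also a smaller matter than it looks. Missed visits are to be rescheduled, and a late visit keeps its label, so it still supplies a date. Only a visit skipped altogether leaves a participant in the study without a stop date, and the documents give no basis for estimating how often that happens.

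**Conclusion.** The SAP's wording is internally inconsistent on which results enter a confirmatory test. Read literally, a Month 30 conversion confirmed at Month 36 is censored at Month 30 unless an unscheduled QFT confirms it, and Section 9.1 and Appendix 6 give never-converters different censoring dates. An inclusive cut-off is probably intended.

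If the literal rule were programmed, H02 would lose about 19% of its expected events: about 145 to 117 at 837 per arm and 8% per year, with power about 95% to 90%. At 10% per year the figures are about 180 to 146, and 98% to 95%. These sizes rest on the plan's inputs, VE of 45% throughout and a constant hazard. They are the cost of one reading, not a forecast of what the sponsor will do. The undefined stop date after a wholly skipped Month 36 visit is a secondary, unquantified gap.

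**What to change.** In SAP 9.1 and in the Appendix 6 rows, replace *prior to* with *on or before* the date of data cut-off. The Month 36 QFT then confirms Month 30 conversions, and the two sections give never-converters the same censoring date.

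As a secondary clarification in SAP 4.3.2 and 7.8, state before unblinding a stop date for a participant who skips Month 36 but remains in the study. One option is the end of the Month 36 visit window, which Protocol Table 4 sets at 14 days after the nominal date. This would serve only as a stop date; SAP 7.7 can continue to apply no windows when identifying sustained conversion.

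The cost is a few words in the SAP and a matching line in the ADaM specification. No new data are needed.
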